4.1.1 Performance of the deep learning model

Preliminary results from the novice test set informed the development of the FAMLI Technology being assessed in the present protocol. This test set contains 249 participant exams in which blind sweeps were obtained by an untrained user on a low-cost, battery-powered device (Butterfly iQ). We compared the deep learning model estimates to biometry obtained by a trained sonographer on a commercial ultrasound (Figure 5). We also compared

model estimates to the gestational age that would have been calculated had only the LMP been available (as is overwhelmingly the case in Zambia and other similar settings where this technology would be used). We found that the model and biometry performed similarly: overall model mean absolute error (MAE) 4.9 days (standard error [SE] 0.29) versus biometry MAE 5.4 days (SE 0.28); difference -0.6 days (95% CI: 1.3, 0.1); $p=0.11$. However, when compared to LMP, the model was clearly superior: model MAE 4.9 days (SE 0.29) versus LMP MAE 17.4 days (SE 1.17); difference -12.7 days (95% CI: -15.0, -10.3); $p<0.001$. Based on the empirical cumulative distribution function of the model error, the proportion of study scans that were correctly classified within 7 days was substantially higher for the model than for LMP (71.9% vs 40.1%; difference 36.1% [95% CI 28.0%, 44.2%]; $p<0.001$). The model similarly outperformed LMP using a 14-day classification window (94.8% vs 55.1%; difference 40.5% [95% CI 33.9%, 47.1%]; $p<0.001$).

Figure 5: Gestational age estimation of deep learning model compared to trained sonographer and last menstrual period (LMP) in the novice test set

^a dashed horizontal lines represent expected accuracy of ultrasound biometry⁴

^b data missing from 22 participants who could not recall their LMP

^c 13 studies from GA by LMP excluded from the plot because the absolute error is truncated at 49 days

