6.3 Study visit procedures

6.3.1 Screening and Randomization

In Zambia, our recruitment activities will begin with community sensitization in the catchment area of the recruitment clinics to educate community members about the study and encourage early presentation for ultrasound. This community and clinic sensitization will be underway prior to initiation of this protocol as a result of other programs ongoing in the catchment areas. In North Carolina, we will advertise the study through flyers, posters, and other electronic or written materials.

Study staff will approach potentially eligible women – either in groups or individually – to inform them about the study (including eligibility criteria). Staff will provide interested women with additional information and referrals to the study clinic for eligibility assessment.

All protocol-specified ultrasound procedures will occur after 13 completed gestational weeks (i.e., 14 0/7 weeks or greater). To be eligible for study participation, women must have documentation of a baseline scan conducted by a trained sonographer prior to 14 weeks gestation to confirm pregnancy location, viability, and gestational age by crown-rump length.

After completing the study informed consent process, study staff will gather targeted information on demographics, health and risk behaviors, medical and obstetrical history, medication use, stress, and nutrition. Participants will undergo blood pressure assessment and anthropometry, including height, weight, mid-upper arm circumference (MUAC), and fundal height (FH). Blood and urine will be collected as detailed in Table 3.

Following final confirmation of eligibility, participant will be assigned a date for each of their follow-up visits in a fashion that ensures approximately equal distribution of study visits across the GA range within each designated visit window. For instance, the primary evaluation window comprises the 14-week period between 14⁰/₇ and 27⁶/₇ gestational weeks, inclusive. Thus, through the randomization procedure, a participant will have a 1 in 14 chance of being allocated to a given gestational week within the primary evaluation window (Table 2). A statistician not otherwise associated with the study will design the scheme and pre-generate the visit schedules for each participant prior to study commencement. Women will be allowed to choose their preferred day of participation within the randomized week.

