6.3.2 Study follow-up

At each study follow-up visit, research staff will collect interval medical and obstetric history, perform anthropometry, measure blood pressure and fundal height, and collect blood and urine specimens for storage and future approved testing (Table 3). An untrained operator will conduct blind sweep procedures using both a commercial ultrasound machine and an approved portable low-cost device. More than one low-cost device may be used for data collection. Next, the sonographer will perform full standard biometry procedures and additional protocol-related ultrasound sweeps using a commercial ultrasound machine. Finally, the trained sonographer will perform biometry and blind sweeps with the low-cost device.

NB: The FAMLI Technology software will not be used to assess gestational age at the time of novice or trained sonographer assessment in an effort to avoid biasing sonographer data collection during biometry. We will also train sonographers not to ask participants their due date or last menstrual period prior to commencing the study scan.

All participants will be followed through delivery. Study staff will document gestational age, vital status, birthweight, and sex at delivery through a combination of medical record review

and participant interview as needed. This visit may occur over the phone or in person. Based on the timing of delivery, not all participants may complete all three planned study follow-up visits.

TABLE 3: Schedule of Evaluations

Visit Number	0.0	1.0	2.0	3.0	4.0
Gestational Age (weeks)	<14	14-27 ⁶	28-36 ⁶	37-40 ⁶	Delivery
ADMINISTRATIVE / REGULATORY PROCEDURES					
Informed consent	•				
Confirmation of eligibility	•				
Collection / review of locator info	•	•	•	•	•
Randomization of visit timing	•				
CLINICAL / BEHAVIORAL PROCEDURES					
Obstetrical and medical history	•	•	•	•	•
Anthropometry	•	•	•	•	
Blood pressure measurement	•	•	•	•	
Fundal height measurement	•	•	•	•	
Physical exam	•				
Untrained operator scan		•	•	•	
Trained sonographer scan		•	•	•	
LABORATORY PROCEDURES					
Urine storage	•	•	•	•	
Blood storage	•	•	•	•	

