6.5.1 Identification and management of clinical complications of pregnancy

When collecting data or performing physical exams, study staff may identify medical or other issues requiring follow-up, treatment, or other clinical care. Similarly, during the course of performing ultrasound procedures on study participants, sonographers may identify medical issues requiring follow-up, treatment, or other clinical care. All team members will be trained on the recognition of adverse events and social harms and what to do if encountered. Safety issues requiring follow-up will be brought to the attention of the senior clinical staff, who will make referrals if the issue is beyond staff knowledge or skills to be able to adequately address.

Potential reasons for clinical referral include, but are not limited to:

- Draining of fluid or concern for ruptured membranes
- Vaginal bleeding or concern for threatened abortion or antepartum hemorrhage
- Abnormal vaginal discharge
- Hypertension
- Fetal anomalies
- Abnormalities of fetal growth
- Oligo- or polyhydramnios
- Intrauterine embryonic or fetal demise

- Malpresentation at or near term
- Suspected extrauterine pregnancy (ectopic)

When possible, the participant will be invited to remain in the study. Additional ultrasound follow-up procedures as determined by obstetrical management recommendations will be provided by study sonographers as requested and free of charge.

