While the primary analysis will compare the index test interpreting blind sweep data as generated by an untrained (novice) sonographer to expert biometry overall, we will also compare the model performance when the blind ultrasound sweeps are generated by an expert sonographer. As in our primary analyses, these analyses will assess model error and clinical reference standard error by comparing estimates to previously established ground truth. Additional secondary analyses will include comparisons in prespecified subsets defined by geography (i.e., Zambia vs North Carolina), medical and obstetrical risk factors (maternal obesity, hypertension, diabetes, fetal growth restriction, oligohydramnios, and polyhydramnios).

Because both the index and reference standard tests are conducted on all women, comparisons of approaches are naturally controlled for all possible time-fixed confounding factors. To account for differential loss to follow-up, if loss to follow-up exceeds 9% and selection bias is suspected, we will employ inverse probability of censoring weights. Censoring weights will be estimated using a pooled logistic regression model fit by maximum likelihood.² We will specify *a priori* a set of possible common causes including demographics, medical, and obstetrical factors, for inclusion as covariates in the model. A list of possible covariates is shown below in Table 1. Continuous covariates will be included using restricted quadratic splines.³

Table 1: Possible covariates for inverse probability of censoring weights modeling

Age, years	BMI, kg/m ²	Estimated gestational age at enrollment, weeks
Education, years	HIV serostatus*	
Marital/partner status	Syphilis serostatus	Transvaginal cervical length, cm
Gravidity (total pregnancies)	Hemoglobin, mg/dL	Study site
Parity (prior deliveries)	Bacteriuria	
Prior miscarriage	Alcohol use in pregnancy	
Prior stillbirth	Tobacco use in pregnancy	
Prior preterm birth	Illicit drug use in pregnancy	

*We will also consider inclusion of HIV-specific covariates through interaction terms (e.g., timing of HIV diagnosis and antiretroviral therapy initiation, antiretroviral therapy regimen, viral load, CD4 count)

References

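### Does the undefined fetal-growth-restriction subset let the scored biometry scan bias its own comparison?

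*SAP*

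**What the plan says.** The SAP's paragraph on additional secondary analyses calls for the index-versus-biometry comparison within subsets by country and by "medical and obstetrical risk factors (maternal obesity, hypertension, diabetes, fetal growth restriction, oligohydramnios, and polyhydramnios". None of the six conditions is defined. Elsewhere, fetal growth appears only in Protocol section 2.0, Table 1 (growth restriction in 0.10 of pregnancies), in a reference title, and in the section 6.5.1 list of reasons for referral, as "Abnormalities of fetal growth".

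On what could feed a label, the Protocol says:
- Section 6.3.1: "All protocol-specified ultrasound procedures will occur after 13 completed gestational weeks". Table 3 accordingly shows no scan at visit 0.0.
- Section 6.3.2, the scored comparator: "Next, the sonographer will perform full standard biometry procedures and additional protocol-related ultrasound sweeps using a commercial ultrasound machine".
- Section 6.3.2, delivery data: "Study staff will document gestational age, vital status, birthweight, and sex at delivery". Table 3 also has obstetrical and medical history at every visit, and fundal height at every visit before delivery.
- Section 6.5.1: "during the course of performing ultrasound procedures on study participants, sonographers may identify medical issues requiring follow-up", and "Additional ultrasound follow-up procedures as determined by obstetrical management recommendations will be provided by study sonographers".

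**The concern.** Growth restriction differs from the other five conditions. A sonographic label compares measured size with ground-truth age. The comparator's signed error, biometry age minus ground-truth age, is nearly the same comparison. If the scored scan supplies the label, the subset is selected on a negative error of the comparator, while the index test's error is selected only so far as the two errors are correlated. Two equally accurate methods would then appear to differ.

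The Protocol leaves two routes open. First, outside IVF the baseline crown-rump length sets the age, so it cannot show a fetus small for that age. In the primary window the scored scan is therefore at the first protocol visit where a sonographic label is possible. Second, a growth problem noticed at a study scan can be referred and followed up by study sonographers, so a diagnosis in the clinical record may begin with the scored scan. At stake is a misleading claim that the index test does better in growth-restricted fetuses.

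**Working it through.** **The plan's own figure.** Protocol section 6.8.2 claims more than 95% power for non-inferiority at zero difference for N of 200 or more, with a 2-day margin. Simulating its model (enrolment age N(74.5, 10.5), error = -7 + 0.1 x age + random error of SD 4 for each method, drawn independently) gives 100% at N=200 and N=400, and about 5% for superiority. The claim is reproduced. Some Table 4 cells away from zero differ by more than 2 points (for example 94.8% against 92% for superiority at tau 3.25, N=400). Rounded coefficients may explain this, and it does not bear on the present point. The documents give no figure for the growth-restriction subset.

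**Inputs for the illustration.**
- Subset size: 0.10 x 400 = 40 women. The 0.10 is a background figure per pregnancy, used here as an assumption.
- Error distribution from section 6.8.2: mean -7 + 0.1 x 74.5 = 0.45 days; SD = sqrt((0.1 x 10.5)^2 + 4^2) = 4.14 days.
- Correlation between the methods' errors, from section 4.1.1: "versus biometry MAE 5.4 days (SE 0.28); difference -0.6 days (95% CI: 1.3, 0.1", reading the lower limit as -1.3. SE of the difference = 1.4/3.92 = 0.357. With SEs 0.29 and 0.28, the absolute errors correlate at (0.29^2 + 0.28^2 - 0.357^2)/(2 x 0.29 x 0.28) = 0.215. Under bivariate normality this corresponds to a signed-error correlation of 0.49 (0.33 to 0.60 allowing for rounding of the interval).

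**Label that partly tracks the scored error.** Let the label score be k x (standardised scored error) + sqrt(1 - k^2) x (independent noise), with the lowest 10% flagged. The methods are equally accurate, so any difference is artefact. The last column is the share of simulated 40-woman subsets whose 95% interval lies wholly below zero (nominal 2.5%).

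| k | Index minus biometry (days) | Interval below zero |
|---|---|---|
| 0 | 0.0 | 3% |
| 0.3 | -0.16 | about 5% |
| 0.5 | -0.57 | 21% |
| 0.7 | -1.27 | 66% |
| 1 | -2.88 | about 100% |

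The documents give no value for k. Over the correlation range 0.33 to 0.60, the k = 1 figure runs from -3.3 to -2.5 days and the k = 0.5 figure from -0.6 to -0.5 days.

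**Label from another visit's biometry.** Split the 4.14-day SD into true size shared by both methods (SD 2.89) and method-specific noise (SD 2.95), and flag the lowest 10% on a scan at a different visit. If biometry noise is independent between visits, the difference is 0.0 days. If it correlates between visits at 0.2, 0.3 or 0.5, the difference is -0.38, -0.61 or -1.15 days. Using another visit therefore removes the artefact only under an independence assumption that the documents do not address. A label that does not use biometry, such as birthweight for ground-truth gestational age, needs no such assumption.

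**The case for a change.** The strongest case for acting is that the subset is called prespecified yet has no definition. The label could then be chosen after results are seen, and one of the available choices gives a spurious advantage of up to 2.9 days, larger than the 2-day margin. The safeguards in Protocol section 6.3.2 (FAMLI output withheld at the scan, sonographers trained not to ask due date or last menstrual period beforehand) protect image acquisition and do not govern classification. A short addition to the SAP would settle it.

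The omission and the mechanism both stand; the step to a defect does not:
- Neither document says the scored scan defines the label. The SAP lists the condition among medical and obstetrical risk factors, beside hypertension and diabetes, so a clinical-history label is a natural reading.
- Calling a fetus small for dates requires the dates. Sonographers who do not ask for them are less likely to originate the diagnosis at the scored scan. The second route is weakened, though not closed, since the comparison can be made afterwards.
- The size depends on k, which has no source in the documents. At k = 0.3 the artefact is 0.16 days. The 10% share and the correlation are also borrowed; the latter comes from a test set whose biometry error averaged 5.4 days, against about 3.3 days in the planning model.
- The SAP states its superiority and equivalence readings for the primary outcome. For these subsets it promises only comparisons.

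**Conclusion.** The concern does not call for a change. The plan omits a definition; it does not prescribe a faulty one. The artefact arises only if whoever builds the subset lets the scored biometry into the label. History, birthweight and gestational age at delivery are recorded, so a label that does not use biometry is available. Each source has its cost: birthweight, for example, needs a reference chart and identifies small size at birth, a somewhat different condition. That choice is ordinary analyst's work, as it is for the other five undefined conditions.

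The possible distortion is about -0.2 to -2.9 days for k from 0.3 to 1, and zero for a label independent of the method-specific errors. This assumes equally accurate methods, 10% flagged, an error correlation of 0.49 and the section 6.8.2 error model. It is confined to one secondary subset of about 40 women. The primary comparison uses every woman with paired estimates at visit 1 and does not involve the label, so its estimate, power and error rates stay as planned. A reader of the eventual subset result should look at how the label was made before reading anything into a difference.
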